Our study team will use social media to reach potentially eligible participants. We have developed a Facebook page for posting IRB-approved study flyers and information for this and other studies in the Traumatic Stress and Health Research Laboratory, <https://www.facebook.com/Duke-Traumatic-Stress-and-Health-Research-Lab-379366159145563/>. We plan to place pictures of our study flyers on the Facebook page, and use Facebook's post boost to draw attention to the post. The post itself will say "Enroll now!" or "Now enrolling!" We will also plan to use Facebook ads to target potential participants within a 50-mile radius of Duke. If any participant contacts the email associated with the Facebook page ([contact]), he/she will be sent an automatic email response.

Based on our previous studies, we expect to screen 250 participants to enroll and randomize 140. Eligibility criteria for the current trial include:

- are an enrolled veteran at the DVAHCS for primary care,
- can read/write/speak fluent conversational English,
- have current AUD (meeting past month DSM-5 criteria), and
- are willing to make a quit attempt and/or reduce alcohol use to low risk levels.

Exclusion criteria are:

- have fewer than 3 days of abstinence,
- have a history of clinically significant alcohol withdrawal, as indicated by 1) a score of 10 or more on the Clinical Institute Withdrawal Assessment of Alcohol (CIWA), 2) past medical alcohol detoxification, or 3) a history of seizures or hallucinations during alcohol withdrawal.
- is current imprisoned or hospitalized on an inpatient psychiatric unit,
- have had a seizure as an adult (e.g., child febrile seizures not exclusionary),
- is unwilling to sign a VA consent form to retrieve medical records, or
- is currently receiving professional behavioral treatment for AUD.

Veterans with a history of clinically significant withdrawal will not be eligible to participate, and will be referred to their providers for evaluation of medical management of clinical detoxification.

D.3. Study Screening Session and Randomization

[figure not shown]

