Cost Measurement. Costs to be collected can be grouped into three broad categories: intervention delivery costs, participant time costs, and health care costs. Intervention costs incurred to develop both interventions will be excluded from the analysis as these costs have already been incurred and are thus “sunk” costs. Intervention Delivery Costs for both conditions will be estimated using both standardized estimates and convenience sampling of support staff and our interventionists. The time it takes to prepare for and execute CBT for SUD is specified in the treatment manual but will be assessed through a data tracking system, surveys, and counselor records to validate these estimates. Similar methods will be used to estimate time spent in identifying veterans with AUD, contacting veterans, and training veterans on the use of the mCM smart phone app. To reduce burden, we will not measure every activity for every subject for every occasion. Instead we will collect a convenience sample of observations toward the beginning and the end of the study to account for the fact that there may be a learning curve effect. The size of the convenience sample will depend on the variability we observe in the activity times—the larger the variability the larger the sample we will collect. In addition to labor costs, materials costs, including the cost of the mCM will be included.

Participant Time Costs (i.e., the opportunity costs to participants). This will include the time spent by participants in using the intervention strategies, techniques, or information. As part of the end-of-treatment follow-up, time spent on the intervention materials other than that involved in the treatment sessions will be assessed. In the intervention arm, the number of videos submitted will be used to assess the time involved in providing bioverification as part of mCM. We will derive participant time cost estimates for each group by combining the time estimates with standard wage estimates adjusted for age, gender, and if possible race, derived from the Statistical Abstract of the United States. Because we chose to conduct the cost-effectiveness analysis from the societal perspective, the use of mean wage rates has higher generalizability and validity than self-reported wages by the subjects. *Health care costs* will be obtained from VA medical records for outpatient, inpatient and medication use one year prior to trial enrollment and through the final follow-up.

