E.1.1. Potential Risks. With regards to completing study measures, there is a risk of discomfort or distress in answering questions. However, distress and discomfort related to questionnaire completion and the psychiatric interview are usually temporary and well-tolerated. Participants are informed that they may refuse to answer any questions while completing the questionnaires. Risks also include discomfort related to alcohol withdrawal. Symptoms of alcohol withdrawal may include headache, insomnia, sweating, shakiness, and rarely, seizures or hallucinations. We will minimize risk of alcohol withdrawal by screening participants at high risk for withdrawal out of the study. However, in case enrolled patients experience alcohol withdrawal that is not reported at the screening visit, we will instruct patients to report symptoms to research staff. There are risks related to participants providing a blood fingerstick. The risks of having a blood puncture includes temporary pain for the needle stick, bruising, and rarely, infection. Some people may experience dizziness, possibly lightheadedness, or rarely, fainting. Finally, there is a potential risk associated with the loss of confidentiality of study data. Because of these risks, the data and safety monitoring plan (DSMP) for this trial focuses on monitoring by the principal investigator (PI), the study physician, and the study coordinator, along with prompt reporting of unexpected and serious adverse events to NIH and to the Institutional Review Board at DUMC.

E.1.2. Potential Benefits. While participants may benefit from quitting or reducing alcohol use, there are no guaranteed benefits to the individual participant and no immediate benefits of the proposed research to others. There are potential benefits to others from the information generated that potentially will be helpful in developing more effective treatment interventions for veterans with AUD.

E.1.3. Protections Against Risk. The study is completely voluntary and participants are informed that they are free to refuse to answer any items on the questionnaires or questions from the interview that they do not wish to answer. They are also informed that they are free to decline participation in any procedure and can withdraw from the study at any time.

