The individuals responsible for data safety and monitoring will be the principal investigator and the project manager. The study physician, [name]., Ph.D., will serve as a Medical Monitor and in that role, provide additional safety monitoring regarding diagnostic and medical issues in enrollment decisions and any medical questions that arise during treatment. [name] is a board-certified psychiatrist with 18 years of experience providing pharmacotherapy in clinical research studies and clinics. He is also a psychiatrist in the Durham VA Health Care System, where he serves as a clinician treating substance use disorders. He has collaborated on research with our group over the past 10 years. [name] has expertise in AUDs and has current and past grant funding from NIH and VA for alcohol-related research. Further data safety and monitoring will be provided by the PI.

As study physician and medical monitor, [name] will ensure participants are medically cleared to participate in this trial and will review all reports of adverse events sent by the study coordinator and evaluate the patient as necessary to determine whether there is any corrective action needed. The Principal Investigator (PI) will be responsible for executing the DSMP, and complying with reporting requirements.

Further data safety and monitoring will be provided by the PI. There will be several ongoing mechanisms for monitoring and reporting of AEs, including SAEs: 1) ongoing participant contact via study personnel; 2) a telephone number provided to participants to report concerns related to study participation; and 3) weekly meetings between the PIs and study personnel. Any adverse events (AEs) will be reported to the IRB in accordance with the Duke University School of Medicine's Human Research Protection Program.

In order to monitor possible negative effects with regards to treatment, including alcohol withdrawal symptoms, participants will be instructed to report any negative effects as soon as possible to research staff; they will have contact information needed to report these problems to study personnel.

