Power calculations provided below were performed with Power Analysis and Sample Size software (PASS, Version 12: NCSS LLC, Kaysville, Utah). The sample size estimate is based on the first hypothesis that the CM intervention will result in higher overall self-reported abstinence rates and fewer days of heavy drinking at 6-months post-randomization. As described in the analysis section, this hypothesis will be tested via linear contrasts specified within the context of MLM analyses. Because this will be tested using repeated-measures data, statistical power will depend on the effective sample size (ESS). The ESS is the number of statistically independent observations available for this study, which is equivalent to the total number of observations (number of participants x number of data collections) adjusted for within-individual correlations. As the intraindividual, or intra-class, correlation (ICC) decreases, the ESS increases. Given that we found an ICC of .20 for 7-day point prevalence measured at posttreatment, 3 months, and 6 months in an RCT with 218 smokers featuring CM as the experimental treatment (R01 CA196304), we anticipate a similar, if not smaller, figure in this trial, given longer intervals between observations. Using this ICC value, with 140 participants with up to 3 observations each, the ESS would be 300. Even with an unexpectedly high 15% attrition at each observation point, such that only 119 complete treatment, 101 6-month follow-up, and 86 12-month follow-up, the ESS for examining linear contrasts would be 227, which would be sufficient to detect treatment effects as small as Cohen's $d = 0.43$ with 90% power. Because the previous trial examining the effect of CM as an adjunct to behavioral treatment found large effects (Cohen's $d = 0.92$; McDonell et al., 2017) on heavy drinking days, our proposed sample size has sufficient statistical power.

G. PROJECT MANAGEMENT PLAN and TIMELINE

The scheduled project timeline is illustrated in Table 5. Members of this multi-disciplinary research team have experience in one or more key components of the

Activity	Year 1				Year 2				Year 3				Year 4				Year 5			
	1	2	3	4	1	2	3	4	1	2	3	4	1	2	3	4	1	2	3	4
Hire/Train Staff	■																			
Recruitment		■	■	■	■	■	■	■	■	■	■	■								
Intervention			■	■	■	■	■	■	■	■	■	■								
Follow-ups: post-txt, 6-and 12-months			■	■	■	■	■	■	■	■	■	■		■	■	■	■			
Data Analysis														■	■	■	■	■	■	■

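### Serious adverse events are found only through study contact or participant report; the VA records already extracted for every participant could cheaply supplement this

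*Combined protocol and SAP*

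**What the plan says.** Section E.2 (Data and Safety Monitoring Plan) names three routes of "monitoring and reporting of AEs, including SAEs: 1) ongoing participant contact via study personnel; 2) a telephone number provided to participants to report concerns"; the last is "3) weekly meetings between the PIs and study personnel". For possible negative effects of treatment, including withdrawal symptoms, it adds that "participants will be instructed to report any negative effects as soon as possible to research staff". The rest of E.2 covers further meetings, review by the principal investigator or project manager, the details recorded for each event, and the medical monitor's review of events sent by the study coordinator. Nothing in Section E uses medical records to find events.

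Those records are collected for another purpose. Under D.6, the data for pricing health care use "will be obtained from VA medical records for outpatient, inpatient and medication use one year prior to trial enrollment and through the final follow-up". D.8.9 draws VA utilization from the VA's central data warehouse, which does not depend on attendance. Table 3 gives the statistical team a healthcare-utilization item at post-treatment, 6 and 12 months. D.2 excludes anyone who "is unwilling to sign a VA consent form to retrieve medical records" and requires enrolment in VA primary care. The stated uses of the records are the cost analysis and the Aim 3 utilization analysis.

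Section F specifies no tabulation of adverse events by arm.

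**The concern.** Contact and the telephone line can bring in a new event. The weekly meetings discuss events already known. An event in someone who has stopped attending therefore reaches the study only if that person calls or later returns.

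The plan foresees some serious events. E.1.1 states: "Symptoms of alcohol withdrawal may include headache, insomnia, sweating, shakiness, and rarely, seizures or hallucinations". The section on psychiatric emergencies describes suicidal or homicidal crises that lead to an emergency room. Events of this kind often leave a hospital record, and the trial will hold many such records without looking at them for safety.

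Two things are at stake. First, an admission that nobody reports does not reach the medical monitor. Second, if one arm stays in contact longer, a table of contact-reported events by arm would partly reflect contact time.

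**Working it through.** **1. Reproduce the plan's attrition.** The power paragraph of Section F assumes 15% loss at each observation point: 140 × 0.85 = 119; 140 × 0.85² = 101.15; 140 × 0.85³ = 85.98. This matches "only 119 complete treatment, 101 6-month follow-up, and 86 12-month follow-up". The plan's effective sample size of 227 also follows if drop-out is monotone and the intraclass correlation is 0.20. With 86 people seen three times, 15 seen twice and 18 seen once: 86 × 3/1.4 + 15 × 2/1.2 + 18 = 184.3 + 25 + 18 = 227.3. The plan's figures thus treat a missed visit as loss from then on. At 12 months 140 − 86 = 54 people (38.6%) are unseen.

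**2. Person-time out of contact in that scenario.** Assumptions: post-treatment falls at 3 months, contact is lost linearly between visits, and a person not seen is out of contact. Retention is 1, 0.850, 0.721 and 0.614 at 0, 0.25, 0.5 and 1 year.

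Area in contact = 0.25 × (1 + 0.850)/2 + 0.25 × (0.850 + 0.721)/2 + 0.5 × (0.721 + 0.614)/2 = 0.231 + 0.196 + 0.334 = 0.762 (unrounded terms). Out of contact: 1 − 0.762 = 0.238, about 24%.

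**3. The same calculation at the retention levels in D.10.** D.10 cites loss near 30% at 12 months in earlier veteran trials, and retention above 80% in the team's own trials. Equal proportional loss per visit is assumed.

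| 12-month retention | Retention at post-treatment / 6 / 12 months | In contact | Out of contact |
|---|---|---|---|
| 80% | 0.928 / 0.862 / 0.800 | 0.880 | 12% |
| 70% | 0.888 / 0.788 / 0.700 | 0.818 | 18% |
| 61% (plan's scenario) | 0.850 / 0.721 / 0.614 | 0.762 | 24% |

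**4. What arm differences would do.** The documents give no retention by arm and no SAE rate. If true risk is equal and events are found only during contact, the apparent CM-to-CBT-alone ratio is the ratio of in-contact areas. Every retention pattern below is assumed.

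| Retention, CM vs CBT alone (post-treatment / 6 / 12 months, %) | Areas | Ratio |
|---|---|---|
| Equal in both arms | 0.762 / 0.762 | 1.00 |
| 90 vs 80 at post-treatment, then 72 and 61 in both | 0.774 / 0.749 | 1.03 |
| 90/80/70 vs 80/64/53 | 0.825 / 0.698 | 1.18 |
| 90/85/80 vs 70/60/50 | 0.869 / 0.650 | 1.34 |

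The last two rows need gaps of 17 and 30 percentage points still present at 12 months.

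**The case against.** The strongest reply is that the gap is smaller than the attrition figures suggest.

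- The 119/101/86 chain is a scenario that the plan itself calls worse than it expects. This stands, so 24% is the pessimistic end of a range and not the plan's forecast.
- Losing contact does not mean that every event is lost. Drop-outs can telephone. In both arms Table 3 schedules suicidality questions and a self-reported utilization measure at post-treatment, 6 and 12 months, and a medical problems checklist at 6 and 12 months. Someone who leaves CBT but returns for a visit is asked. This stands too. A reader might infer that serious harms in drop-outs go wholly unreported; the documents support only that they may be missed. None of these measures reaches people who never return, and E.2 does not link the utilization measure or the checklist to safety reporting.
- A reader might infer that more events are missed with CBT alone. Hypothesis 1a and its definition in Section F concern CBT sessions completed, not follow-up attendance. CM lasts eight weeks plus a practice week, and the follow-up payments and retention methods are the same in both arms. The roughly ten weekly app prompts request breath readings, and nothing says that they ask about adverse events. The direction is plausible but is not derived from the plan.
- Some foreseen events are already well covered. The emergency-room escort follows a staff assessment, so the study knows of it. The quit date falls during weekly sessions, and people at high risk of withdrawal are screened out.
- No between-arm safety test is planned, so no planned result is biased.

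What survives is narrower: for people out of contact, the plan names no source of safety data except their own call, although another source is already being extracted.

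**Conclusion.** The point holds as an inexpensive improvement in safety ascertainment. As written, SAE detection depends on study contact or participant report. About 12% to 24% of first-year person-time would be out of contact, depending on whether 12-month retention is 80% or the 61% of the pessimistic scenario. These figures assume linear loss between visits and post-treatment at 3 months. They are shares of person-time, not of events.

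A reader might turn 24% into a share of SAEs missed, or raise it by supposing higher risk after drop-out. The first step assumes the same risk after drop-out and no telephoned reports. The second needs a risk multiplier that the documents do not give. Similarly, an apparent excess on CM of 1.18 to 1.34 depends entirely on assumed retention by arm. The ratio is 1.00 with equal attrition and about 1.03 if the arms differ only at post-treatment. Capture could differ by arm; whether it would, and by how much, cannot be derived from the plan.

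The primary endpoint and the other efficacy analyses are unaffected.

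**What to change.** **Section E.2.** Add a further source of events as a supplement to contact reporting. At each utilization extract already scheduled (post-treatment, 6 and 12 months), list VA admissions and emergency visits, and deaths where the record holds them. Do this for every randomised participant, whether or not they attend and identically in all arms, and pass the list to the existing medical monitor.

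**Section F.** Add one descriptive table of SAEs by randomised arm (CM vs CBT alone; long-term incentive vs none) over a fixed 12 months. Show record-identified events separately from contact-reported events. No test is needed.

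**To confirm first.**
- That the records consent covers safety use.
- Whether extraction continues after a participant withdraws or is withdrawn; the documents do not say.
- That emergency visits and deaths are in the extract; D.6 names neither.
- Whether extracts are run at each time point or retrospectively, since this decides how soon the monitor sees an event.

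**Cost.** One query on largely existing data, some monitor time and one table, with no new visits or staff. Some listed admissions will be unrelated to the study. Periodic extracts are not real-time. Non-VA care is still missed, including the university emergency room named in the section on psychiatric emergencies, and continues to rest on contact and self-report.

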As shown in Figure 3, proposed is a 2X2 factorial randomized clinical effectiveness trial testing the effects of combining CM as an adjunct to state-of-the-art, evidence-based CBT (CBT + CM vs. CBT only) and the effects of a single, long-term incentive for bioverified abstinence/no heavy drinking at 6-months follow-up (Long Term Incentive vs. No Incentive). All patients will be referred to standard aftercare and encouraged to participate in 12-step programs following the intervention. Use of aftercare and other health care utilization will be collected based on objective measures (VA electronic medical record) and participant report. Health-related quality of life will be collected at each follow-up. The primary endpoint (AIM 1) will be number of heavy drinking days in the past 30 days at the 6-month follow-up. Cost effectiveness analysis (AIM 2) will be performed using quality-adjusted life years (QALY) as the outcome. The utility of a long-term incentive (AIM 3) will be tested by examining use of aftercare and other alcohol-related treatment and heavy drinking days in the past 30 days at the 6 and 12-month follow-ups.

D.2. Patient Identification, Eligibility, and Recruitment

Patients will be identified from the Durham VA Health Care System (DVAHCS) using the hospital's computerized medical record. Records will be screened for AUD. After mailing introductory materials with an opt-out number, we will contact those who do not opt out via telephone to explain the study and recruit them for participation. If necessary, in order to reach female veterans, we can oversample women for the screening mailouts.

Figure 3. Trial Design

We will also utilize reactive recruitment methods as needed to reach potentially eligible veterans. For example, we will seek referrals from the DVAHCS Substance Use Disorders Clinic. In order to reach female veterans, we will seek referrals from the Women's Health Clinic. In addition, we will post IRB-approved flyers and brochures throughout the DVAHCS catchment area, especially in clinic areas and Vet Centers. In addition, we will post, if necessary, flyers and brochures in the community, in local restaurants, laundromats, university student centers, etc. We will also use online classified advertisements such as Craigslist.com to reach potential participants.

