Potential participants who discuss the study with study personnel will complete a brief phone screen to assess potential eligibility. Veterans who are potentially eligible will attend a screening session where they will complete diagnostic interviews, self-report measures, urine drug screen and alcohol breathalyzer to determine inclusion. Participants who screen in will be randomized at the first treatment session to one of two treatment conditions (CBT+mCM vs. CBT alone) and to one of two long term incentive conditions (abstinence incentive at 6 months vs. No incentive). Stratified permuted block randomization assignments will be performed using a computerized sequence generated by the study statistician before the study starts. The sequence will be password-protected so that only the statistician and other study staff who do not have patient contact will have access to the sequence. We will stratify on the presence of comorbid non-tobacco SUD.

D.4. Interventions

D.4.1. Cognitive-Behavioral Therapy for Substance Use Disorders

We will use the VA CBT for SUD protocol (DeMarce, Gnys, Raffa, & Karlin, 2014) to provide in-person treatment in both study arms. CBT will be provided by a therapist with at least a Master's degree in mental health (e.g., psychology, social work) who has reviewed CBT for SUD training materials. To prevent confounding from therapist effects, study therapists will treat cases in both study arms. CBT sessions will be weekly over 12 weeks as shown in Figure 3. Following the standard of care for AUDs, all participants will be referred to aftercare and encouraged to participate in 12-step programs following completion of the 12-session CBT intervention (Proctor & Herschman, 2014).

Figure 3. Timeline for Intervention and Follow-Ups

D.4.2. Mobile Contingency Management for AUD Procedures

As shown in Figure 3, participants will begin one week of practice mCM monitoring at session two of CBT so they can troubleshoot any difficulties they have using the app. The beginning of contingent reinforcement (i.e., the target quit date) is scheduled for the same date as session three of CBT (week 3), which will provide eight weeks of mCM before the end of CBT. Patients who attend all weekly appointments will have two sessions of CBT occurring after mCM ends to assist in preventing relapse when monetary reinforcement is removed.

Table 2. Virtual Scratch-Off Lottery Ticket Reinforcement Amounts				

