The PI will meet at least weekly with study personnel to discuss participants' reactions to the intervention, proper delivery of the intervention, and any adverse events or unanticipated problems. Monthly meetings between the investigators and the project manager will allow for ongoing progress reports, including the number of participants currently involved in the study groups, attrition rates, and scheduled data collection from participants, as well as notification and review of any AEs. Safety monitoring for adverse events will be conducted in real time by the PI and/or project manager. The following information about adverse events will be collected: 1) the onset and resolution of the AE, 2) an assessment of the severity or intensity, 3) an assessment of the relationship of the event to the study (definitely, probably, possibly or not related), and 4) action taken (e.g., none, referral to physician, start or increase concomitant medication). The PI will determine the severity of the event, will assign attribution to the event, and will monitor the event until its resolution.

F. STATISTICAL ANALYSES AND POWER CONSIDERATIONS

Variables of interest will be examined using means, standard deviations, and distributions (for continuous variables) and their frequencies (for categorical variables). For normally distributed outcome variables, linear statistical models will be used by default. However, examination of residuals and Q-Q plots will be undertaken to determine whether generalized linear modeling may be more appropriate. We will first conduct preliminary analyses to ensure that there are no differences across treatment groups with respect to gender, age, educational history, socioeconomic status, baseline alcohol consumption, PTSD symptoms, and depressive symptoms. In addition, we will evaluate potential effects of psychiatric variables on the treatment response. We do not expect differences to arise on these measures as a result of randomization. Nevertheless, we will potentially use covariate adjustment to address unanticipated differences in baseline variables. We will conduct sensitivity analyses to determine how variability in demographic/baseline variables influence estimates of treatment effects (Thabane et al., 2013).

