Aim 1: To examine the first hypothesis that CM will be associated with greater treatment engagement and treatment completion than the control condition, treatment engagement will be defined as the number of counseling sessions completed, with treatment completion defined as completion of all 12 counseling sessions. Potential group differences in treatment engagement as a function of counseling sessions completed will be examined using independent *t*-tests. Contingency-table analysis will be used to examine whether a greater proportion of the CM participants complete the treatment in comparison to the control group. The second hypothesis is that CM will be associated with higher rates of self-reported abstinence and fewer heavy drinking days at 6 and 12 months. MLM will be used to model each of these outcomes. Specifically, logistic MLM will be

conducted to model abstinence as a function of treatment, time (categorized as end of treatment, 6 months, 12 months), and the interaction between treatment and time. Randomization to long-term abstinence incentive will be covaried. Linear contrasts will be specified at each time point to examine the hypothesis that CM will result in higher abstinence rates than CBT alone at 6 and 12 months. A similar count-based model (e.g., Poisson, negative binomial) will be conducted to analyze number of days of heavy drinking (per 30 days). In addition to modeling the effects of treatment, time, and the interaction between treatment and time, number of days of heavy drinking recorded at baseline and randomization to the long-term abstinence incentive will be covaried. Again, linear contrasts will be derived at each time point to compare treatment effects at 6 and 12 months.

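### Covariates beyond the core model depend on chance baseline differences and analyst discretion; the stratification factor is in neither Aim 1 drinking model and baseline drinking is missing from the abstinence model

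*Combined protocol and SAP*

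**What the plan says.** The opening of Section F (Statistical Analyses and Power Considerations) sets out a sequence. "We will first conduct preliminary analyses to ensure that there are no differences across treatment groups", on these variables: "gender, age, educational history, socioeconomic status, baseline alcohol consumption, PTSD symptoms, and depressive symptoms". It says that no differences are expected under randomisation, and then that "we will potentially use covariate adjustment to address unanticipated differences in baseline variables". No test, threshold or list of candidate covariates is given, and nothing says whether an adjusted or an unadjusted result would be the main one. The next sentence promises sensitivity analyses of how baseline variables affect the treatment estimates.

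Other places fix part of the model:

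- Section D.1: "The primary endpoint (AIM 1) will be number of heavy drinking days in the past 30 days at the 6-month follow-up".
- Section F, Aim 1, heavy drinking days: treatment, time and their interaction, and in addition "number of days of heavy drinking recorded at baseline and randomization to the long-term abstinence incentive will be covaried".
- Section F, Aim 1, abstinence: treatment, time and their interaction, with one further term: "Randomization to long-term abstinence incentive will be covaried".
- Section F, Aim 3 repeats this pattern with CM arm as the other factor. Baseline heavy drinking days are in the count model and not in the abstinence model.
- Section D.3: "We will stratify on the presence of comorbid non-tobacco SUD". This factor does not appear in any of these models.

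**The concern.** Under randomisation a baseline difference between arms is a chance event, so comparing the arms does not show which covariates belong in the model. What makes a covariate useful is how strongly it predicts the outcome, and the stated rule ignores that. A strong predictor that happens to be balanced is left out, and a weak one that happens to differ is put in.

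The gap is widest for abstinence, which Section F counts among the primary treatment outcomes and which the sample-size paragraph also relies on. Baseline alcohol consumption is one of the seven screened variables. As written, it would enter the abstinence model only if it happened to differ between arms.

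The adjustment is also optional. Section D.3 gives the statistician access to the allocation sequence, and nothing requires the covariates to be settled before outcomes are seen by arm. More than one p-value depends on this: Section F, Aim 2 makes the choice between cost-effectiveness and cost-minimisation analysis hang on significance of the primary outcome.

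**Working it through.** **1. The plan's own figures.** The power paragraph of Section F states that "with 140 participants with up to 3 observations each, the ESS would be 300", with an ICC of 0.20. The formula is ESS = n·m / (1 + (m − 1)·ICC).

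- Full data: 420 / 1.4 = 300, as stated.
- After attrition to 119, 101 and 86, there are 86 people with three observations, 15 with two and 18 with one: 258/1.4 + 30/1.2 + 18 = 184.3 + 25 + 18 = 227.3. The plan states 227.
- Power at d = 0.43 with 113.5 per arm and two-sided alpha 0.05 (assumed, since neither is stated) is 0.8996. The plan states 90%.

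These figures reproduce and contain no covariate term, so the point does not alter them.

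**2. How often chance would trigger adjustment.** Assume seven independent tests, each at 0.05. The chance of at least one flag is 1 − 0.95^7 = 0.302.

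**3. Effect on type I error and power, heavy-drinking-days type of model.** This was simulated with a linear model at one time point, 70 per arm, no dropout and independent normal covariates. Baseline drinking is always in the model (R² 0.20, assumed). The six other variables are tested for balance at 0.05, and their joint R² is varied from 0 to 0.5 (assumed). There were 20,000 runs per setting, with a Monte Carlo standard error of about 0.0015 for type I error. A flag occurred in 26–27% of runs, in line with 1 − 0.95^6 = 0.265.

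Type I error at nominal 0.05:

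| Joint R² of the six | All fixed in advance | Mechanical test-then-adjust | Smaller p kept, only when a variable is flagged | Free choice, core or fully adjusted |
|---|---|---|---|---|
| 0 | 0.050 | 0.049 | 0.052 | 0.059 |
| 0.1 | 0.052 | 0.047 | 0.053 | 0.068 |
| 0.3 | 0.050 | 0.041 | 0.055 | 0.079 |
| 0.5 | 0.048 | 0.034 | 0.054 | 0.086 |

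The mechanical rule falls below nominal because large imbalances are either adjusted away or absent. The unadjusted estimate that remains varies less than its standard error implies.

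Power at d = 0.43 in the same set-up:

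| Joint R² of the six | All fixed in advance | Mechanical test-then-adjust |
|---|---|---|
| 0.1 | 0.84 | 0.81 |
| 0.3 | 0.94 | 0.82 |

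A repeat of the simulation gave 0.83 against 0.80, and 0.93 against 0.82. These values rest on 140 people at a single time point. They compare the two rules with each other and should not be set against the plan's 90%, which rests on the ESS of 227.

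**4. Abstinence type of model.** Here no baseline covariate is fixed and all seven are tested. Baseline drinking has R² 0.25 or 0.5 and the other six jointly 0.1 (assumed). There were 12,000 runs per setting, with a Monte Carlo standard error of about 0.002.

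- Mechanical rule: type I error 0.034–0.040 at a balance threshold of 0.05, and 0.021–0.035 at thresholds of 0.10 and 0.20.
- Smaller p-value kept when a variable is flagged: 0.052–0.058 across these thresholds.

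**The case against.** The strongest reply is that the primary-endpoint model is already largely fixed. Baseline heavy drinking days, likely to be an important predictor, and the incentive arm are both in it by name. The trigger for anything further is baseline data, examined first, and not outcome results. The plan also promises sensitivity analyses on baseline variables. Most of this stands. A reader might infer from the opening of Section F that the primary model as a whole is left open; the Aim 1 text shows that only the additional covariates are.

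A reader might also infer that testing and then adjusting inflates type I error. The simulation does not support that: applied mechanically, the rule sits at or below nominal. Larger values require a free choice between models after both results are known. The text leaves room for that but does not describe it.

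It can further be said that adjusting for an imbalance that has occurred is better than ignoring it. That is right. Among runs with a flag, the core model alone had type I error of 0.057 to 0.095 as the joint R² rose from 0 to 0.5, while the fully adjusted model had 0.046 to 0.055. But this argues for fixing prognostic covariates in advance, which gives the same protection without a trigger.

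The 30% also deserves caution. The plan names neither a test nor a threshold, and some of the seven variables are probably correlated (PTSD with depressive symptoms, education with socioeconomic status).

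Three things remain unanswered: extra covariates have no criterion, the sensitivity-analysis sentence does not make discretionary adjustment secondary, and the two omitted terms are not supplied elsewhere.

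**Conclusion.** The point holds as a matter of incomplete pre-specification. Covariates beyond the core terms would be chosen from chance baseline differences, with discretion. Baseline drinking is not fixed in the abstinence models, and the stratification factor is in none of the drinking-outcome models.

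On the plain reading, the cost is power: about 0.03 at a joint R² of 0.1 and about 0.11 to 0.12 at 0.3. Type I error is about 0.03 to 0.05 under the mechanical rule with a 0.05 threshold, and at most about 0.058 if discretion is limited to flagged variables. It reaches about 0.06 to 0.09 only under free choice between core and fully adjusted results. The documents do not exclude that choice, and they do not say it will be made.

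These sizes rest on assumed R² values, an assumed two-sided 0.05 level, independent covariates and a linear single-time-point stand-in for the planned count and logistic multilevel models. The documents give no figure for how strongly the SUD stratum or the screened variables predict drinking, so the true loss could lie anywhere in or near the range shown.

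**What to change.** Change the wording of Section F as follows.

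- Remove the baseline comparison as a trigger for adjustment, and present baseline characteristics by arm descriptively.
- For every Aim 1 and Aim 3 outcome model, name the covariates: the other randomised factor, the comorbid non-tobacco SUD stratum and baseline drinking. For abstinence this means adding a baseline drinking term.
- List any further prognostic variable by name, before outcome data are analysed by arm.
- State that the model with these terms gives the main result, and label every other adjusted analysis as a sensitivity analysis.

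This is a free improvement. Baseline drinking is collected at screening and the stratum is known at randomisation, so no new data are needed. The stated sample size, ESS and power do not change.
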